### 1.2.3.2 Clinical Development of ONC201

Due to preclinical results, ONC201 is currently being investigated in phase I and II trials in patients with refractory solid tumors including glioblastoma as well as in patients with relapsed/refractory non-Hodgkin's lymphoma, relapsed/refractory acute leukemias and high-risk myelodysplastic syndromes. Many of these trials are ongoing, but results from the first-in-human phase I trial of ONC201 in patients with refractory solid tumors are promising (2, 4). The trial enrolled 28 patients with 15 different types of tumors including prostate cancer, endometrial cancer, ovarian cancer, colon cancer, gallbladder cancer and sarcoma. In this heavily treated population (average of 5-6 prior treatments), researchers found prolonged stable disease in many patients, as well as disease reduction in others patients, most notably in those with endometrial or prostate cancer. This trial also evaluated the safety and tolerability of ONC201. The recommended phase 2 dose (RP2D) was determined to be 625mg by mouth q3 weeks and dosing was subsequently adjusted to weekly dosing due to pharmacokinetic studies.

[figure not shown]
There have been no deaths attributed to study drug. There have been no SAEs assessed by the investigators as "probably" or "definitely" related to study drug, and no discontinuation of ONC201 due to toxicity has been reported. The most common AEs reported as possibly related to ONC201 were mild/moderate nausea, vomiting, anorexia, pyrexia and fatigue.

More than 70 patients with advanced solid tumors and hematological malignancies were evaluated in phase I clinical trials and no serious side effects were found attributable to ONC201. Grade I adverse events that have been observed and reported include fever, nausea, vomiting, fatigue, and elevated serum amylase that were attributed as possibly-related to ONC201. One Grade II allergic reaction occurred that was managed with standard

*Abbreviated Title: ONC201 in advanced cancers*

*Version Date: 06/17/2020*

medications. One Grade III event neutropenia was transiently observed. No other Grade III or IV events were reported so far.

**Figure 4:** Waterfall plot of best fractional change in tumor size relative to baseline on a lesion-by-lesion basis. Best change in lesion size is defined as maximal reduction or minimal increase in sum of longest dimensions of target lesions relative to pretreatment assessment.

*Image from Stein et al, 2017(4).*

The lesion-by-lesion results of this phase 1 study were recently reported (**Figure 4**) (2, 4). In this phase I study, 3 of 5 patients with endometrial cancer had stable disease by RECIST criteria (> 4 months in 2 and >10 months in one). The [name] lab has also confirmed that ONC201 had a similar effect on the killing of various

endometrial cancer cell lines (data not shown) as it did on breast cancer cell lines. Based on these results we propose to include a cohort of patients with endometrial cancer in our trial.

Only one triple negative breast cancer patient was recruited for the phase 1 study, and unfortunately had disease progression while on ONC201. Nevertheless, the preclinical data on breast cancer cell lines performed by the drug developer and confirmed by the [name] lab is encouraging that women with breast cancer may derive clinical benefit from ONC201.

#### **1.2.4 Pharmaceutical Manufacturer Updates**

##### 1.2.4.1 ONC201 Investigator Brochure v6 November 2019

As of October 31, 2019, the majority of adverse events (AEs) experienced by participants on clinical trials who received ONC201 were mild or moderate in severity. The most frequently reported AEs of any grade (in greater than 25% of patients) were fatigue, nausea, headache and vomiting. These AEs were generally Grade 1/2, with fatigue being the only Grade 3/4 AE that occurred in more than one patient on the ONC013 study (17.4%).

*Abbreviated Title: ONC201 in advanced cancers*

*Version Date: 06/17/2020*

Eleven patients experienced serious adverse events (SAEs) that were considered possibly related to ONC201. The list of SAEs reported by investigators that were attributed as possibly-related to ONC201 by the investigator are:

- Grade 1: Fatigue, vomiting
- Grade 3: Encephalopathy, cognitive impairment, neutropenia, upper respiratory infection, respiratory distress, pneumonia, stroke, tremor, fatigue, bone pain, anorexia, weakness
- Grade 4 Dysphagia, dyspnea

Two suspected unexpected serious adverse (SUSAR) events occurred at a dose of 625mg daily. Both events were encephalitis that occurred on the investigator-initiated trial NCT02392572 in patients with MDS or AML and are considered dose-limiting toxicities(DLT). No other DLTs occurred in other indications or at lower doses both as monotherapy or in combination with other agents. Only one dose reduction (625mg to 500mg) occurred in one patient with a Grade 3 neutropenia assessed by the PI as possibly related to ONC201. However, upon re-challenge neutropenia did not recur.

Based on the clinical safety data summarized above, ONC201 administered at the doses and schedules below 625mg daily appears to be well tolerated in adults and children.

## 2 ELIGIBILITY ASSESSMENT AND ENROLLMENT

### 2.1 ELIGIBILITY CRITERIA FOR COHORT 1: HORMONE RECEPTOR POSITIVE BREAST CANCER

#### 2.1.1 Inclusion Criteria

- 2.1.1.1 Patients must have histologically confirmed persistent or recurrent invasive metastatic hormone receptor positive, HER2 normal breast cancer for which standard curative measures do not exist or are no longer effective. Hormone receptor positive is defined as estrogen receptor (ER) positive  $\geq 10\%$  by immunohistochemistry (IHC) and/or progesterone receptor (PR) positive  $\geq 10\%$  by IHC. HER2 will be considered negative per ASCO-CAP guidelines (HER2 test result as negative if a single test (or both tests) performed show: 1) IHC 1+ as defined by incomplete membrane staining that is faint/barely perceptible and within  $>10\%$  of the invasive tumor cells; 2) IHC 0 as defined by no staining observed or membrane staining that is incomplete and is faint/barely perceptible and within  $\leq 10\%$  of the invasive tumor cells; or 3) ISH negative based on: a) Single-probe average HER2 copy number  $<4.0$  signals/cell or b) Dual-probe HER2/CEP17 ratio  $<2.0$  with an average HER2 copy number  $<4.0$  signals/cell) and HER2 testing must have been performed in a laboratory accredited by the College of American Pathologists (CAP) or another accrediting entity.
- 2.1.1.2 Patients must have measurable disease, per RECIST 1.1. See Section 6.3.1 for the evaluation of measurable disease.
- 2.1.1.3 Patients must have at least one lesion deemed safe to biopsy and be willing to undergo mandatory biopsies.
- 2.1.1.4 HR+BC patients must have received prior treatment with at least 2 lines of hormonal treatment (SERM, AI, or fulvestrant) and deemed ineligible for further hormonal

*Abbreviated Title: ONC201 in advanced cancers*

*Version Date: 06/17/2020*

therapy . Patients may have received prior chemotherapy and there is no limit to the number of prior chemotherapy.

- 2.1.1.5 Age  $\geq 18$  years.
- 2.1.1.6 ECOG performance status 0 or 1
- 2.1.1.7 Adequate renal function, defined as serum creatinine  $\leq 1.5$  X upper limit of normal (ULN), or measured creatinine clearance  $\geq 60$  mL/min/1.73 m^2.
- 2.1.1.8 Adequate hepatic function, defined as AST and ALT levels  $\leq 3$  X ULN and total bilirubin  $< 1.5$  X ULN, unless known diagnosis of Gilbert's syndrome, where bilirubin  $\leq 5$  mg/dL will be permitted. Gilbert's syndrome will be defined as elevated unconjugated bilirubin, with conjugated (direct) bilirubin within the normal range and less than 20% of the total. Total bilirubin will be permitted up to 5 mg/dL, if patients have historical readings consistent with the definition of Gilbert's syndrome prior to entering study.
- 2.1.1.9 Adequate bone marrow function, defined as absolute neutrophil (ANC)  $\geq 1,500/\text{mm}^3$  ( $\geq 1.5 \times 10^6/\text{L}$ ), platelet count  $\geq 75,000/\text{mm}^3$  ( $\geq 75 \times 10^6/\text{L}$ ), and hemoglobin  $\geq 9$  mg/dL (transfusion to obtain hemoglobin  $\geq 9$  mg/dL within 24 hours prior to dosing is allowed).
- 2.1.1.10 Patients must be able to swallow oral medications (capsules) without chewing, breaking, crushing, opening or otherwise altering the product formulation.
- 2.1.1.11 The effects of *ONC201* on the developing human fetus are unknown. For this reason and because *imipridone* agents are known to be teratogenic, female patients must either be of non-reproductive potential (i.e., post-menopausal by history:  $\geq 60$  years old and no menses for  $\geq 1$  year without an alternative medical cause; OR history of hysterectomy, OR history of bilateral tubal ligation, OR history of bilateral oophorectomy) or must have a negative serum pregnancy test upon study entry and agree to use contraception or abstinence during the study and for and for at least 4 weeks after the final dose of any study-related medications. Male patients must use at least two forms of contraception during the study and for at least 4 weeks after the final dose of any study-related medications or have a partner who is not of reproductive potential. (See Section 4.2)
- 2.1.1.12 Ability of subject to understand and the willingness to sign a written informed consent document.

## **2.1.2 Exclusion Criteria**

- 2.1.2.1 Patients who have received chemotherapy in the previous 3 weeks (6 weeks for nitrosoureas or mitomycin); other investigational agents within 3 weeks or a PD1/PDL1 agent within 4 weeks prior to first dose of study treatment.
- 2.1.2.2 Patients who have undergone radiotherapy within 4 weeks of first dose of study treatment.
- 2.1.2.3 Patients with a history of another invasive malignancy within the last 3 years.
- 2.1.2.4 Patients with symptomatic brain metastases or leptomeningeal involvement. Patients with asymptomatic or brain metastases that have been treated with radiation at least 4 weeks prior to first dose of study treatment are allowed.

**Abbreviated Title:** *ONC201 in advanced cancers*

**Version Date:** 06/17/2020

- 2.1.2.5 History of allergic reactions attributed to compounds of similar chemical or biologic composition to *imipridones* or other agents used in study.
- 2.1.2.6 Patients with a mean QTcF interval of > 500 msec or receiving therapeutic agents known to prolong the QT interval
- 2.1.2.7 Known history of cardiac arrhythmias including uncontrolled atrial fibrillation, tachyarrhythmias or bradycardia, history of congestive heart failure, or myocardial infarction or stroke in the previous 3 months will be excluded.
- 2.1.2.8 Known history of gastrointestinal illnesses that would preclude the absorption of ONC201, which is an oral agent
- 2.1.2.9 Patients with bone metastases who have initiated denosumab or bisphosphonate therapy within 28 days prior to Cycle 1 Day 1.
- 2.1.2.10 Pregnant women are excluded from this study because ONC201 has the potential for teratogenic or abortifacient effects. Because there is an unknown but potential risk for adverse events in nursing infants secondary to treatment of the mother with ONC201, breastfeeding should be discontinued if the mother is treated with ONC201. These potential risks may also apply to other agents used in this study.
- 2.1.2.11 HIV-positive patients on combination antiretroviral therapy are ineligible because of the potential for pharmacokinetic interactions with ONC201.
- 2.1.2.12 Patients who have known active Hepatitis B, or Hepatitis C infections.

## 2.2 ELIGIBILITY CRITERIA FOR COHORT 2: TRIPLE NEGATIVE BREAST CANCER

### 2.2.1 Inclusion Criteria

- 1.1.1.1 Patients must have histologically or cytologically confirmed persistent or recurrent invasive, metastatic triple negative breast cancer (TNBC) for which standard curative measures do not exist or are no longer effective. TNBC, defined as ER negative (ER < 10%), PR negative (PR <10%). HER2 will be considered negative per ASCO-CAP guidelines (HER2 test result as negative if a single test (or both tests) performed show: 1) IHC 1+ as defined by incomplete membrane staining that is faint/barely perceptible and within >10% of the invasive tumor cells; 2) IHC 0 as defined by no staining observed or membrane staining that is incomplete and is faint/barely perceptible and within ≤10% of the invasive tumor cells; or 3) ISH negative based on: a) Single-probe average HER2 copy number <4.0 signals/cell or b) Dual-probe HER2/CEP17 ratio <2.0 with an average HER2 copy number <4.0 signals/cell) and HER2 testing must have

- been performed in a laboratory accredited by the College of American Pathologists (CAP) or another accrediting entity.
- 1.1.1.2 Patients must have received at least one line of prior chemotherapy in the metastatic setting.
  - 2.2.1.1 Patients must have measurable disease, per RECIST 1.1. See Section 6.3.1 for the evaluation of measurable disease.
  - 2.2.1.2 Patients must have at least one lesion deemed safe to biopsy and be willing to undergo mandatory biopsies.
  - 2.2.1.3 Eligible patients may or may not have received prior chemotherapy and there is no limit to the number of prior chemotherapy. Patients are also eligible if they have received treatment with immunotherapy, such PD-1 inhibitors, PD-L1 inhibitors or CTLA4 inhibitors.
  - 2.2.1.4 Age  $\geq 18$  years.
  - 2.2.1.5 ECOG performance status 0 or 1
  - 2.2.1.6 Adequate renal function, defined as serum creatinine  $\leq 1.5$  X upper limit of normal (ULN), or measured creatinine clearance  $\geq 60$  mL/min/1.73 m^2.
  - 2.2.1.7 Adequate hepatic function, defined as AST and ALT levels  $\leq 3$  X ULN and total bilirubin  $< 1.5$  X ULN, unless known diagnosis of Gilbert's syndrome, where bilirubin  $\leq 5$  mg/dL will be permitted. Gilbert's syndrome will be defined as elevated unconjugated bilirubin, with conjugated (direct) bilirubin within the normal range and less than 20% of the total. Total bilirubin will be permitted up to 5 mg/dL, if patients have historical readings consistent with the definition of Gilbert's syndrome prior to entering study.
  - 2.2.1.8 Adequate bone marrow function, defined as absolute neutrophil (ANC)  $\geq 1,500/\text{mm}^3$  ( $\geq 1.5 \times 10^6/\text{L}$ ), platelet count  $\geq 75,000/\text{mm}^3$  ( $\geq 75 \times 10^6/\text{L}$ ), and hemoglobin  $\geq 9$  mg/dL (transfusion to obtain hemoglobin  $\geq 9$  mg/dL within 24 hours prior to dosing is allowed).
  - 2.2.1.9 Patients must be able to swallow oral medications (capsules) without chewing, breaking, crushing, opening or otherwise altering the product formulation.
  - 2.2.1.10 The effects of *ONC201* on the developing human fetus are unknown. For this reason and because *imipridone* agents as well as other therapeutic agents used in this trial are known to be teratogenic. Female patients must either be of non-reproductive potential (i.e., post-menopausal by history:  $\geq 60$  years old and no menses for  $\geq 1$  year without an alternative medical cause; OR history of hysterectomy, OR history of bilateral tubal ligation, OR history of bilateral oophorectomy) or must have a negative serum pregnancy test upon study entry and agree to use contraception or abstinence during the study and for and for at least 4 weeks after the final dose of any study-related medications. Male patients must use at least two forms of contraception during the

*Abbreviated Title: ONC201 in advanced cancers*

*Version Date: 06/17/2020*

study and for and for at least 4 weeks after the final dose of any study-related medications or have a partner who is not of reproductive potential. (See Section 4.2).

2.2.1.11 Ability of subject to understand and the willingness to sign a written informed consent document.

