### Eligibility:

#### Selected Inclusion Criteria

- Histologically confirmed metastatic breast cancer or endometrial cancer with appropriate IHC testing and confirmation of HER2 non-amplification required for the breast cancer cohorts (cohorts 1 and 2)
- Age 18 years or older
- Female and male breast cancer patients are eligible for the breast cancer cohorts
- ECOG 0 or 1
- Measurable metastatic disease with  $\geq 1$  biopsiable lesion with willingness to undergo a biopsy
- Cohort 1 (HR+BC) requires prior treatment with  $\geq 2$  lines of hormonal treatment. No prior treatment required for cohorts 2/3 (TNBC and EC).
- Adequate hematopoietic, hepatic and renal function

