## 1 INTRODUCTION

### 1.1 STUDY OBJECTIVES

#### 1.1.1 **Primary Objective**

- **Cohort 1 HR+BC** - To determine the progression free survival at 8 months (PFS by RECIST) of ONC201 in patients with refractory, metastatic hormone receptor positive breast cancer
- **Cohort 2 TNBC** - To determine the overall response rate (ORR; CR + PR by RECIST) of ONC201 in patients with metastatic triple negative breast cancer
- **Cohort 3 Endometrial Cancer** - To determine the ORR of ONC201 in patients with advanced or metastatic endometrial cancer

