## 2.3 ELIGIBILITY CRITERIA FOR COHORT 3: ENDOMETRIAL CANCER

### 2.3.1 Inclusion Criteria

- 2.3.1.1 Patients must have histologically or cytologically confirmed persistent or recurrent advanced or metastatic invasive endometrial cancer (EC) for which standard curative measures do not exist or are no longer effective.
- 2.3.1.2 Patients must have measurable disease, per RECIST 1.1.. See Section **6.3.1** for the evaluation of measurable disease.
- 2.3.1.3 Patients must have at least one lesion deemed safe to biopsy and be willing to undergo mandatory biopsies.
- 2.3.1.4 Women with endometrial cancer must have had at least one prior line of therapy in the metastatic/recurrent setting but there is no limit to the number of prior chemotherapy lines. Patients are eligible if they have received treatment with immunotherapy, such PD-1 inhibitors, PD-L1 inhibitors or CTLA4 inhibitors.
- 2.3.1.5 Age  $\geq 18$  years.
- 2.3.1.6 ECOG performance status 0 or 1
- 2.3.1.7 Adequate renal function, defined as serum creatinine  $\leq 1.5$  X upper limit of normal (ULN), or measured creatinine clearance  $\geq 60$  mL/min/1.73 m^2.
- 2.3.1.8 Adequate hepatic function, defined as AST and ALT levels  $\leq 3$  X ULN and total bilirubin  $< 1.5$  X ULN, unless known diagnosis of Gilbert's syndrome, where bilirubin  $\leq 5$  mg/dl will be permitted. Gilbert's syndrome will be defined as elevated unconjugated bilirubin, with conjugated (direct) bilirubin within the normal range and less than 20% of the total. Total bilirubin will be permitted up to 5 mg/dL, if patients have historical readings consistent with the definition of Gilbert's syndrome prior to entering study.
- 2.3.1.9 Adequate bone marrow function, defined as absolute neutrophil (ANC)  $\geq 1,500/\text{mm}^3$  ( $\geq 1.5 \times 10^6/\text{L}$ ), platelet count  $\geq 75,000/\text{mm}^3$  ( $\geq 75 \times 10^6/\text{L}$ ), and hemoglobin  $\geq 9$  mg/dL (transfusion to obtain hemoglobin  $\geq 9$  mg/dL within 24 hours prior to dosing is allowed).
- 2.3.1.10 Patients must be able to swallow oral medications (capsules) without chewing, breaking, crushing, opening or otherwise altering the product formulation.

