## 9 CLINICAL MONITORING

As a sponsor for clinical trials, FDA regulations require the CCR to maintain a monitoring program. The CCR's program allows for confirmation of: study data, specifically data that could affect the interpretation of primary and secondary study endpoints; adherence to the protocol, regulations, ICH E6, and SOPs; and human subjects protection. This is done through independent verification of study data with source documentation focusing on:

- Informed consent process
- Eligibility confirmation

*Abbreviated Title: ONC201 in advanced cancers*

*Version Date: 06/17/2020*

- Drug administration and accountability
- Adverse events monitoring
- Response assessment.

The monitoring program also extends to multi-site research when the CCR is the coordinating center.

This trial will be monitored by personnel employed by a CCR contractor. Monitors are qualified by training and experience to monitor the progress of clinical trials. Personnel monitoring this study will not be affiliated in any way with the trial conduct.

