### Cohort 3: Advanced endometrial cancer

Published data from several trials report response rates of 8 to 15% for second line treatment in patients with advanced endometrial cancer (18-21). As such, it would be desirable if new treatments are associated with at least a 12-15% response rate for further consideration. In patients with advanced endometrial cancer, the primary objective of this study would be to determine if using ONC201 would rule out a 5% response rate and result in a response rate consistent with 25%. As such, the trial will be conducted using a single stage design (42) in order to rule out an unacceptably low PR+CR rate of 5% ( $p_0=0.05$ ) in favor of an improved response rate of 25% ( $p_1=0.25$ ). Based on a one-sided exact binomial test, 25 patients would have 90% power to rule out 5% and result in findings consistent with a 25% PR + CR rate. At the end of the study, we would form the two-sided 80% and 95% CI about the observed percentages of both response (PR+CR) and clinical benefit (SD+PR+CR). 3 responses (PR + CR) in 25 patients (12.0%) has a two-sided 80% CI of 4.5-24.8%, which is potentially worthy of further consideration, while 4 responses in 25 (16.0%) has a two-sided 80% CI of 7.2-29.5%, which would be sufficiently interesting for further evaluation. As an early stopping rule, after 13 evaluable patients have been enrolled, if there are 0 patients with clinical benefit (SD+PR+CR), then the cohort would end accrual since the 90% one-sided upper CI bound on 0/13 is 16.2%, which would be marginally too low for further interest. Both the PR+CR and SD+PR+CR rates can be formed at the interim time for descriptive purposes as well as for evaluation for early stopping. The study may need to pause accrual to evaluate if clinical benefit in the first 13 patients exceeds the early stopping rule.

Any secondary evaluations performed will be done in an exploratory fashion, with results presented without any formal adjustment for multiple comparisons.

*Abbreviated Title: ONC201 in advanced cancers*

*Version Date: 06/17/2020*

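### Cohort 2's inclusion list makes prior metastatic chemotherapy both mandatory and optional, and the précis waives the prior treatment that cohort 3 requires

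*Combined protocol and SAP*

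**What the plan says.** Four statements on prior therapy matter here, all in the current version of the combined protocol and SAP.

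- Section 2.2.1 (cohort 2), item numbered 1.1.1.2: "Patients must have received at least one line of prior chemotherapy in the metastatic setting".
- Section 2.2.1 (cohort 2), item 2.2.1.3: "Eligible patients may or may not have received prior chemotherapy and there is no limit to the number of prior chemotherapy". The item goes on to allow prior immunotherapy.
- Section 2.3.1 (cohort 3), item 2.3.1.4: "Women with endometrial cancer must have had at least one prior line of therapy in the metastatic/recurrent setting", with no upper limit on chemotherapy lines and a similar immunotherapy sentence.
- Précis, Selected Inclusion Criteria: "No prior treatment required for cohorts 2/3 (TNBC and EC".

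For comparison, cohort 1 item 2.1.1.4 requires two or more lines of hormonal treatment and then says of chemotherapy: "Patients may have received prior chemotherapy and there is no limit to the number of prior chemotherapy".

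**The concern.** Within one list, cohort 2 requires chemotherapy for metastatic disease and also says that eligible patients need not have had any. The précis sides with the second statement and extends the waiver to cohort 3, where the full criterion says the opposite.

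What is at stake is who may be treated. Section 1.2.1.2 describes single-agent chemotherapy as the standard for metastatic TNBC, with response rates around 30-35%. A patient admitted under 2.2.1.3 with no chemotherapy for metastatic disease could receive ONC201 before that standard. If such patients are wanted, that should be an explicit decision by the sponsor.

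Monitoring does not fully close the gap. Section 9 lists "Eligibility confirmation" among the items verified against source. In cohort 3 that check has a clear criterion to work from, so an enrollment made from the précis alone can be caught. In cohort 2 the full criteria carry both statements, so the monitor has no single clear rule.

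**Working it through.** The defect is one of wording, so the main check sets the texts side by side. The design figures are then recomputed to see whether any depends on the wording.

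**Step 1. A test patient in cohort 2.** Take a patient with metastatic TNBC who has had no chemotherapy at all and meets every other criterion.

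| Text | Prior chemotherapy | Result |
|---|---|---|
| Item 1.1.1.2 | one or more lines for metastatic disease, mandatory | ineligible |
| Item 2.2.1.3 | optional | eligible |
| Précis | none required | eligible |

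One statement makes prior chemotherapy mandatory and two do not. Item 2.2.1.3 could be reconciled with 1.1.1.2 if it referred only to neoadjuvant or adjuvant treatment, but its wording carries no such limit.

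**Step 2. Does anything else settle cohort 2?**

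- The cohort 2 objective in section 1.1.1 reads "of ONC201 in patients with metastatic triple negative breast cancer", with no line of therapy.
- The cohort 2 benchmark in section 10.2 (30-35%) is for recurrent or metastatic TNBC, again with no line stated.
- The cohort 1 sentence on chemotherapy is nearly the same as 2.2.1.3. It causes no conflict there, because cohort 1 has no mandatory chemotherapy line.
- Cohort 3 pairs a mandatory prior line with no upper limit and omits the optional clause.

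The last two points suggest that the optional clause in cohort 2 is leftover wording. That is an inference; the protocol does not say so.

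**Step 3. Cohort 3.** Item 2.3.1.4 and the précis contradict each other directly. Section 10.2 decides between them: "Published data from several trials report response rates of 8 to 15% for second line treatment in patients with advanced endometrial cancer". A second-line benchmark fits a mandatory prior line, so the précis is the text to correct. If 1.1.1.2 governs cohort 2, the précis is wrong for that cohort as well.

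**Step 4. The design figures.** For a rule of at least r responses in n patients, P(X ≥ r) is the sum over k from r to n of C(n,k) p^k (1−p)^(n−k).

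- Cohort 2 (section 10.2: n = 29, p0 = 0.25, p1 = 0.45, 11 responses of interest): P(X ≥ 11) is 0.829 at 45%, against the stated power of 82%, and 0.086 at 25%.
- Cohort 3 (section 10.2: n = 25, p0 = 0.05, p1 = 0.25, 4 responses of interest): P(X ≥ 4) is 0.904 at 25%, against the stated 90%, and 0.034 at 5%.

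Both cohorts' figures reproduce from their own inputs, and prior-therapy status is not among those inputs. Correcting the text so that 1.1.1.2 and 2.3.1.4 govern changes none of them.

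**The case against.** The strongest reply is that the text is less ambiguous than it looks. Inclusion criteria are cumulative. Item 1.1.1.2 is mandatory, while 2.2.1.3 is permissive and does not claim to waive another item. A patient without metastatic chemotherapy therefore fails a listed requirement, and the harm arises only if staff overlook it. The parallel cohort 3 wording points the same way. The précis is headed as a selection, and the full criteria are in section 2. On this view the matter is close to editorial.

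Much of this stands. The mandatory reading is the more natural one, the précis error in cohort 3 is minor, and counting statements for and against does not settle what was intended. But 2.2.1.3 is not silent: it describes who is eligible, the précis agrees with it, and no text ranks the two items. Staff should not have to infer an eligibility rule from how other cohorts were drafted.

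A second objection is that the cost may be understated if the sponsor chooses to admit untreated TNBC patients. That is fair for that option alone. Whether 25% is then the right null rate becomes an open question, because section 10.2 does not give the line of therapy behind its 30-35%. As an illustration, the chance of 11 or more responses in 29 is 0.086 at a true rate of 25%, 0.229 at 30% and 0.438 at 35%. These rates come from the protocol's benchmark and are not predictions for ONC201.

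**Conclusion.** The concern holds. Cohort 2's operative criteria cannot all be followed as written, and the précis contradicts cohort 3's criterion outright. The cohort 2 conflict is the one that matters; the cohort 3 part is minor, because the full criterion is clear and only the summary is wrong.

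The effect is confined to metastatic TNBC patients with no chemotherapy for metastatic disease. The document gives no basis for estimating how many would present. No stated sample size, power or response threshold changes under the main correction. That item 1.1.1.2 was meant to govern is the likely reading but an assumption, which only the sponsor can confirm. The correction should be made, as it decides who may be treated.

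**What to change.** The sponsor confirms whether item 1.1.1.2 governs cohort 2.

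- **If it does:** delete from 2.2.1.3 the clause that makes prior chemotherapy optional, and keep the absence of an upper limit and the immunotherapy sentence. Change the précis to require one or more prior chemotherapy lines for metastatic disease in cohort 2, and one or more prior lines of therapy for metastatic or recurrent disease in cohort 3.
- **If untreated patients are intended in cohort 2:** delete 1.1.1.2, correct the précis for cohort 3 only, and state why a 25% null rate suits the broader population.

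The first option costs one confirmation and a wording amendment in two places, the cohort 2 inclusion list and the précis. Sample size, thresholds, power and analysis stay as they are. The second needs the same confirmation and wording edits, plus the short check on the null rate.
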